## **3.2 Analysis time points**

### **3.2.1 First and last dose of iv BRV**

Unless otherwise noted, all references to the first dose of iv BRV in this SAP refer to the first dose of iv BRV during EP0065.

Unless otherwise noted, all references to the last dose of iv BRV in this SAP refer to the last dose of iv BRV in this study.

### **3.2.2 First and last dose of oral BRV**

Unless otherwise noted, all references to the first dose of oral tablet or solution BRV in this SAP refer to the first dose of oral tablet or solution of BRV dispensed during EP0065.

Unless otherwise noted, all references to the last dose of oral tablet or solution BRV in this SAP refer to the last dose of oral tablet or solution of BRV dispensed during EP0065.

### **3.2.3 Relative day and time**

Relative Day is defined as the day relative to the first infusion of BRV. Relative day will not be calculated for partial dates.

If the current date occurred on or after the day of first dose of iv BRV and prior to or on the day of last iv BRV dose, the relative day will be calculated as the current date minus the date of first dose of iv BRV plus 1 (eg, the day of first dose of iv BRV will be Day 1).

If the current date occurred prior to the first dose of iv BRV, the relative day will be calculated as date of first dose of iv BRV minus the current date (eg, the day prior to first dose of iv BRV will be Day -1).

If the current date occurred after the last dose of iv BRV, the relative day will be calculated as the current date minus the date of last dose of iv BRV including a "+" to denote post-treatment days (eg, the day after the last dose of iv BRV will be Day +1).

In order to have a better insight into the times of AEs, laboratory samples, ECG and vital signs collections relative to the administration of BRV, the relative time will be calculated, by subtracting the time of first iv BRV administration from the start time of the event. The relative time will be displayed in hours and minutes for relative times  $\leq 24$  hours before and after the first iv BRV administration. For relative times  $> 24$  hours the relative times will be calculated in days as described above.

### **3.2.4 Relative time from previous iv infusion**

Relative time from previous iv infusion initiation will be derived for AE listings. It will be displayed in hours and minutes and will be calculated using the following formula:

---

relative time from previous iv infusion initiation  
= *AE start time* – previous infusion start time

### 3.2.5 Analysis periods

This study consists of a Screening Period, an IOB Treatment Period, an iv PK Period, a Follow-up Period and a Safety (BRV-free) Period, see [Section 2.3](#) for more details on these periods.

Start of Screening Period is defined as the date of enrollment and end of Screening Period is defined as immediately before first allocated BRV treatment.

Start of IOB Treatment Period is defined as the date of first allocated oral BRV treatment and end of IOB Treatment Period is defined as immediately before first iv BRV treatment.

Start of iv PK Period is defined as the date and time of first allocated iv BRV treatment and end of iv PK Period is defined as 12 hours after start of last iv BRV treatment.

Start of Follow-up Period is defined as 12 hours after start of last iv BRV treatment and end of Follow-up Period is defined for the following scenarios:

- Subjects who transition study: as TC-1
- Subjects who do not transition and do not down-titrate: as end of study
- Subjects who down-titrate: as 12 hours after start of last down-titration treatment.

Only subjects who down-titrate have a Safety (BRV-free) Period. Start of Safety Period is defined as immediately after the end of Follow-up Period (>12 hours after start of last down-titration treatment) and end is defined as end of study.

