After subjects have completed PK sampling with 2 iv BRV infusions, the Investigator may adjust the BRV dose, but the adjusted dose must not exceed 5mg/kg/day (rounded) for OLB and RxB subjects and 4mg/kg/day for IOB and IIB subjects (with the maximums not to exceed 200mg/day). During the iv PK Period, BRV may only be administered intravenously. Enrollment will be sequential by descending age beginning with Cohort 1. For each cohort, the first half will receive the 15-minute infusion. The Data Monitoring Committee (DMC) will then meet to review safety and, as available, PK data (Figure 5–1). After the DMC safety review, the remaining half in that cohort will receive iv BRV as a bolus (up to 2-minute infusion) and the next cohort may begin the 15-minute infusion. Subjects may receive bolus infusions only after subjects in the preceding cohort have completed bolus infusions and the DMC have reviewed these data. The DMC will meet no less than approximately every 6 months commensurate with enrollment.

Figure 5–1: Schematic of sequential cohort enrollment during the iv PK Period

DMC=Data Monitoring Committee; inf=infusion; iv=intravenous; PK=pharmacokinetic

Telephone Contact (TC)-1 will occur 1 to 3 days after completing the final iv BRV dose in the iv PK Period to facilitate reporting of infusion-site related AEs.

The schedules for PK sampling, 12-lead ECGs, and vital sign assessments during the iv PK Period are provided in Table 5–2 (15-minute infusion), and Table 5–3 (bolus [up to 2-minute infusion]).

Down-Titration Period (up to 4 weeks) and Safety (BRV-free) Period (2 weeks)

Subjects who receive ≥4 doses of BRV during either the IOB Treatment Period or the iv PK Period and who do not plan to continue treatment with BRV or who discontinue from the study will enter a Down-Titration Period. Subjects who have received <4 doses of BRV may have BRV down titrated at the discretion of the Investigator. During the Down-Titration Period, subjects will have their BRV dose reduced by a maximum of half the dose every week for a maximum of 4 weeks until a dose of 1mg/kg/day (50mg/day for subjects with body weights ≥50kg) is reached. Subjects not able to receive oral BRV for down titration, may receive iv BRV for down titration. In the latter circumstance, the subjects may receive more than 10 consecutive

doses of iv BRV in accordance with the Investigator's discretion. A 2-week Safety (BRV-free) Period will follow the final dose of BRV.

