^b Blood samples for PK analyses will be collected for the initial BRV infusion and 1 subsequent BRV infusion only. Blood samples should be collected after completion of the ECG and the vital sign measurements and from a region of the body not used for the iv BRV administration.

^c Only BP to be collected at 2 hours post initiation of infusion. Additional vital sign monitoring, specifically BP is necessary if a low PCS BP value occurs at 2 hours after the start of an infusion.

Table 5–4: Schedule of study assessments for Down-Titration and Safety (BRV-free) Periods (subjects not continuing into the Long-Term, Open-Label Study)

Visit	Down-Titration		Safety (BRV-free)
	TC-2 ^a	V13	TC-3 ^b
Assessments			
Concomitant medications including AEDs	X	X	X
Physical examination (brief)		X	
Neurological examination (brief)		X	
Body height		X	
Vital signs (BP, pulse rate, RR, temperature)		X	
12-lead ECG		X	
Clinical chemistry, hematology, and endocrinology		X	
Urinalysis (for subjects for whom sample collection is feasible)		X	
Pregnancy testing (urine; for females of CB potential)		X	
AEs	X	X	X
Withdrawal criteria	X		
C-SSRS ^c		X	
Collect oral BRV		X	

AEDs=antiepileptic drug; AEs=adverse events; BP=blood pressure; BRV=brivaracetam; CB=childbearing; C-SSRS=Columbia-Suicide Severity Rating Scale; ECG=electrocardiogram; RR=respiratory rate; TC=telephone contact; V=Visit

^a This TC is only applicable to subjects with a Down-Titration Period of more than 2 weeks. The TC should be conducted approximately half way through the Down-Titration Period.

^b This TC is only applicable for subjects who have attended Visit 13 and will be conducted approximately 2 weeks after the final dose of BRV.

^c The C-SSRS will be assessed only in subjects ≥ 6 years of age. The C-SSRS versions to be used are specified in Section 10.3.3.

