 - Investigators should attempt to obtain information on subjects in the case of withdrawal; subjects who withdraw from the study without down titration of BRV should complete the Visit 13 (Table 5–4).

For subjects considered lost to follow up, the Investigator should make an effort (at least 1 phone call and 1 written message to the subject), and document his/her effort (date and summary of the phone call and copy of the written message in the source documents), to complete the final evaluation. All results of these evaluations and observations, together with a narrative description of the reason(s) for removing the subject, must be recorded in the source documents. The CRF must document the primary reason for withdrawal.

Investigators should contact the Medical Monitor, whenever possible, to discuss the withdrawal of a subject in advance.

6.3.1 Potential drug-induced liver injury investigational medicinal product discontinuation criteria

Subjects with potential drug-induced liver injury (PDILI) must be assessed to determine if the investigational medicinal product (IMP) must be discontinued. In addition, all concomitant medications and herbal supplements that are not medically necessary should also be discontinued.

The PDILI criteria below require immediate and permanent discontinuation of IMP:

- Subjects with either of the following:
 - ALT or AST $\geq 5 \times \text{ULN}$
 - ALT or AST $\geq 3 \times \text{ULN}$ and coexisting total bilirubin $\geq 2 \times \text{ULN}$

The PDILI criterion below requires immediate discontinuation of IMP:

- Subjects with ALT or AST $\geq 3 \times \text{ULN}$ who exhibit temporally associated symptoms of hepatitis or hypersensitivity. Hepatitis symptoms include fatigue, nausea, vomiting, right upper quadrant pain or tenderness. Hypersensitivity symptoms include fever (without clear alternative cause), rash, or eosinophilia (ie, $>5\%$).

The PDILI criterion below allows for subjects to continue on IMP at the discretion of the Investigator.

- Subjects with ALT or AST $\geq 3 \times \text{ULN}$ (and $\geq 2 \times$ baseline) and $< 5 \times \text{ULN}$, total bilirubin $< 2 \times \text{ULN}$, and no eosinophilia (ie, $\leq 5\%$), with no fever, rash, or symptoms of hepatitis (eg, fatigue, nausea, vomiting, right upper quadrant pain or tenderness).

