- The number and percentage of subjects completing the iv PK Period
  - Completed is receiving at least one iv BRV dose during the iv PK Period.
- The reasons for discontinuing during the iv PK Period.
- The number and percentage of subjects starting down-titration (Follow-up Period)
  - Start is defined by having at least one down-titration BRV treatment.
- The number and percentage of subjects starting the Safety Period
  - A subject is considered as starting the Safety Period if their date of study termination is at least 12 hours after the last BRV treatment received during down-titration.

A summary of discontinuations due to AEs for the SS-iv will present the number and percentage of subjects who discontinued this study due to AEs overall, and by type of AE. The table will be repeated for the SS.

The following listings will be provided for all subjects screened: subjects who did not meet study eligibility criteria, subject disposition, subject analysis sets, subjects excluded from at least one analysis set, study discontinuation, and visit dates.

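### The SAP's analysis periods count off-drug events after an untapered stop as Follow-up, and leave two boundaries underivable for IOB children who are never infused

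*SAP*

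**What the plan says.** SAP 3.2.5 defines the periods used for tabulation. Follow-up starts 12 hours after the start of the last iv dose. It ends at TC-1 for children who move to another study. For the other two routes the rules are "Subjects who do not transition and do not down-titrate: as end of study" and "Subjects who down-titrate: as 12 hours after start of last down-titration treatment". The SAP then adds: "Only subjects who down-titrate have a Safety (BRV-free) Period". The Safety Period row in SAP 5.1 follows the same idea, counting a child if "their date of study termination is at least 12 hours after the last BRV treatment received during down-titration". For IOB children, "end of IOB Treatment Period is defined as immediately before first iv BRV treatment".

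The protocol is less uniform. Section 5.1, at the end of its down-titration text, says: "A 2-week Safety (BRV-free) Period will follow the final dose of BRV". Section 6.3 says that "subjects who withdraw from the study without down titration of BRV should complete the Visit 13", and section 8.6 also applies Visit 13 to withdrawals that need no down-titration. Table 5-4 puts TC-3 in its Safety (BRV-free) column, with a footnote making it "only applicable for subjects who have attended Visit 13 and will be conducted approximately 2 weeks after the final dose of BRV". Section 8.7 says the same.

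Under SAP 10.2.1, each AE belongs to the period in which it began, and TEAEs are tabulated by study period for the SS. SAP 3.10, which lists changes to the protocol-defined analysis, does not mention the restriction.

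**The concern.** A column headed Safety (BRV-free) should hold events that began after BRV was stopped. Under SAP 3.2.5 it holds them only for children who tapered. Events in a child who stopped without a taper appear under Follow-up, beside those of children continuing BRV or on falling doses, and the by-period tables have no on-drug or off-drug split to separate them. The protocol makes this route foreseeable: children are normally to receive 1 or 2 iv doses, and down-titration is left to the Investigator below 4 doses.

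The second problem is a gap in the definitions. The SS includes children who received only oral BRV. For an IOB child who stops before any infusion, the end of the IOB Treatment Period and the start of Follow-up are both fixed by an iv dose that was never given. Later AEs and down-titration doses then fall in the IOB Treatment Period or in no period.

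**Working it through.** **1. The plan's own durations.** The maximum period lengths in Protocol 5.1 are Screening 10, IOB 10, iv PK 6, down-titration 28 and BRV-free 14 days.
- Study: 10 + 10 + 6 + 28 + 14 = 68 days.
- BRV: 10 + 6 + 28 = 44 days.

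Both match Protocol 5.1.1, so 14 days is the BRV-free length to use.

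**2. SAP 3.2.5 applied to each route.**

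| Route | End of IOB period (IOB children) | Start of Follow-up | End of Follow-up | Safety Period |
|---|---|---|---|---|
| iv, moves to long-term study | defined | defined | TC-1 | none |
| iv, down-titrates | defined | defined | 12 h after last taper dose | yes |
| iv, stops without taper | defined | defined | end of study | none |
| IOB, no iv, down-titrates | not derivable | not derivable | 12 h after last taper dose | yes |
| IOB, no iv, no taper | not derivable | not derivable | end of study | none |

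The start and end of Screening and the start of the IOB period are defined without an iv dose.

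**3. What Follow-up contains.**
- Child who moves on: from 12 h to TC-1 at 1 to 3 days, so 1 − 0.5 = 0.5 to 3 − 0.5 = 2.5 days, on BRV.
- Child who down-titrates: up to about 28 days, on falling BRV.
- Child who stops without a taper and has TC-3 at day 14: 14 − 0.5 = 13.5 days, on no BRV.

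**4. Which IOB children meet the gap.** Twice-daily oral dosing for 2 to 10 days gives 2 × 2 = 4 to 10 × 2 = 20 doses. An IOB child who completes 2 days thus normally reaches the 4-dose trigger in Protocol 5.1, which counts IOB doses, and falls in the fourth row. SAP 5.1 counts that child as starting down-titration (its Follow-up row) at the first taper dose, but SAP 3.2.5 gives no date for the start of Follow-up. SAP 3.2.6 computes oral exposure separately for the IOB and Follow-up Periods, so exposure is affected too.

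**5. Outputs affected.** These are the by-period TEAE tables on the SS (SAP 10.2.1), the oral exposure summaries by period (SAP 10.1) and the Safety Period row (SAP 5.1). The SS-iv AE tables combine all periods and do not change. The iv PK Period boundaries are not in question.

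**The case against.** The strongest reply is that the SAP follows one reading of the protocol. Section 1 describes the BRV-free period together with down-titration for children with 4 or more doses. Section 5.1 places its sentence at the end of the down-titration text. Section 10.1.4 lists Visit 13 and TC-3 only for pregnant subjects who are tapered. This stands in part: a reader might infer that the SAP plainly contradicts the protocol, but the protocol is itself ambiguous. It does not remove the problem, because Table 5-4 and sections 6.3, 8.6 and 8.7 schedule the BRV-free contact for untapered withdrawals. Those data are foreseen by the protocol, so the list-only rule in SAP 3.1 does not exclude them.

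Other stronger readings also go too far:
- A reader might infer that never-infused IOB children have no valid boundaries at all. Only two fail.
- A reader might compare the Follow-up lengths above as a measure of bias. The planned tables give subject incidence and event counts without exposure adjustment, so such a ratio says nothing about them.
- A reader might infer that withdrawal effects are being hidden. Among children new to BRV, untapered stoppers are mainly those with at most 3 doses. For OLB and RxB children the position is less clear, because section 5.1 counts doses in the IOB and iv PK Periods while section 1 names no period.
- A child who neither moves to another study nor tapers is not necessarily off drug. An RxB child might return to prescribed BRV.

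It is also fair that AE listings give onset dates and times, so in a study of about 50 children individual off-drug events can be found.

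**Conclusion.** The point holds in a limited form. Followed as written, SAP 3.2.5 places off-drug AEs of untapered stoppers in Follow-up with children on BRV, and it cannot date two boundaries for IOB children who never receive iv BRV. The first is a narrowing of a period that the protocol describes inconsistently; the second is a gap in the SAP's definitions.

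The size is about 13.5 off-drug days per untapered stopper, assuming that TC-3 takes place at 2 weeks, that it marks that child's end of study, and that the child does not continue BRV elsewhere. The documents do not say how many children are affected; it may be few or none. If SS and SS-iv have the same number of subjects, the second problem does not arise.

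The primary safety set's all-period tables and the iv PK Period summaries are unaffected. The correction is still worth making, because AEs throughout the study are a primary safety variable and Protocol 12.4.1.1 promises AE summaries by period on the SS.

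**What to change.** - In SAP 3.2.5 and the Safety Period row of SAP 5.1, start the Safety (BRV-free) Period 12 hours after the last BRV dose of any route, for every subject who stops BRV and does not continue it in a long-term study or by prescription, whether or not they tapered. End Follow-up there. Nothing changes for children who taper.
- An untapered stopper after iv dosing then has no Follow-up time, so AEs collected at TC-1 count as BRV-free. State this, or show untapered subjects as a separate row.
- For IOB subjects with no iv dose, end the IOB Treatment Period and start Follow-up at the first down-titration dose, which agrees with SAP 5.1. If there is no down-titration, end the IOB Treatment Period 12 hours after the last oral dose.
- List the change in SAP 3.10, and reconcile Protocol sections 1, 5.1 and 10.1.4 with Table 5-4 and sections 6.3, 8.6 and 8.7.

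The cost is SAP wording and period-derivation code, with no new data collection. Children who continue BRV by prescription would have to be identified from the medication records already collected.

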### 3.2.6 Exposure duration

In EP0065 study medication is defined as iv BRV.

The date and time of first study medication is defined as the start of first iv BRV infusion date and time according to the standard CRF page. The date and time of last study medication is defined as the start of last iv BRV infusion reported on the standard trial termination eCRF.

Days with unknown or zero dosing for the respective BRV formulation (iv, tablet, oral solution, oral, all) which occur between the start and end date of the respective BRV formulation will be included in the exposure calculation. For example, a day with missing or zero dosing between the first and last iv BRV dose will be included in the iv BRV exposure duration (days) and iv BRV exposure duration (hours) calculation.

The iv BRV exposure duration will be calculated separately in hours and days. Duration of iv BRV exposure in days will be calculated using the following formula:

$$\begin{aligned} &\text{iv BRV exposure duration (days)} \\ &= \text{start date and time of the last iv BRV} \\ &\quad - \text{start date and time of the first iv BRV} + 1 \text{ day} \end{aligned}$$

Duration of iv BRV exposure in hours will be calculated using the following formula:

$$\begin{aligned} &\text{iv BRV exposure duration (hours)} \\ &= \text{start date and time of the last iv BRV} \\ &\quad - \text{start date and time of the first iv BRV} + 1 \text{ hour} \end{aligned}$$

The duration of oral BRV exposure will be calculated in days only by administration method (tablets or oral solution) and over both administration methods separately for the IOB Treatment Period and Follow-up Period. The duration of oral BRV will be calculated separately for each period using the following formulas:

$$\begin{aligned} &\text{Oral BRV exposure duration from tablets during period (days)} \\ &= \text{end date of last BRV tablet during period} \\ &\quad - \text{start date of first BRV tablet during period} + 1 \text{ day} \end{aligned}$$

$$\begin{aligned} &\text{Oral BRV exposure duration from oral solution during period (days)} \\ &= \text{end date of last oral solution BRV during period} \\ &\quad - \text{start date of first oral solution BRV during period} + 1 \text{ day} \end{aligned}$$

$$\begin{aligned} &\text{Overall Oral BRV exposure duration during period (days)} \\ &= \text{end date of last oral BRV during period} \\ &\quad - \text{start date of first oral BRV during period} + 1 \text{ day} \end{aligned}$$

The overall BRV duration (oral BRV and iv BRV exposure) in days will be calculated using the following formula:

$$\begin{aligned} &\text{Overall BRV exposure duration (days)} \\ &= \text{end date of latest BRV (either oral or iv)} \\ &\quad - \text{start date of first BRV (either oral or iv)} + 1 \text{ day} \end{aligned}$$

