#### 4.2.5 Handling of study medication with partial or missing date

No imputation should be performed for missing study medication start dates. This field on the eCRF should not be partial or missing.

For partial or missing date of last dose of study medication, the following imputation rules will be applied for the purpose of calculating overall exposure:

- If the day is missing (but month and year available), impute the last dose date as the earliest of the last day of the month or the date of last contact reported on the trial termination eCRF; if day and month are both missing (only year available), impute the last dose date as the earliest of the last day of the year or the date of last contact on the trial termination eCRF.
- If a subject died and has a partial or missing last dose date, the last dose date is to be set to the date of death. If there is a partial date of last dose and the month/year are prior to the month and year of the date of death, follow partial date imputation rules.
- If the last dose date is completely missing and no information could be obtained from data cleaning exercises, the last dose date should be imputed as the date of last contact according to the study termination eCRF. A review of the data for subjects with completely missing last dose dates should be performed to ensure that the imputation does not result in an unrealistic value for duration of exposure.

Imputed date of last dose dates should only be used for calculation of the duration of exposure. The date as recorded on the eCRF should be presented in subject data listings (no imputed dates should be included in subject data listings).

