### 10.1 Extent of exposure

The duration of iv BRV exposure, as defined in [Section 3.2.6](#), will be summarized as continuous parameters (once in hours and once in days) for the iv PK Period on the SS-iv. The number and percentage of subjects who received 0, 1, 2, 3, ..., 10 BRV infusions will be displayed for the SS-iv. Handling of missing study medication data is described in [Section 4.2.5](#). Mean iv BRV dose (mg/kg) will be summarized as continuous parameters for the iv PK Period for the SS-iv. This table will be presented by age groups for all subjects, by infusion duration and by weight (<50kg and ≥50kg).

The duration of overall oral BRV exposure, oral BRV exposure from tablets and oral BRV exposure from oral solution as defined in [Section 3.2.6](#), will be summarized as continuous parameters (in days) separately for the IOB Treatment Period and the Follow-up Period for the SS.

The overall BRV duration (oral BRV and iv BRV exposure), as defined in [Section 3.2.6](#), will be summarized as a continuous parameter (in days) for the SS-iv and SS respectively.

The following listings will be provided for the SS unless otherwise stated:

- study medication administration, which displays relevant information about the BRV iv dosing including the start and stop time of each infusion, the target dose and whether the target dose was delivered.
- BRV exposure, which displays relevant information about the BRV iv and oral dosing including the number of infusions received, and the total BRV exposure.
- Oral BRV dosing during study
- Oral BRV administration from oral solution
- Oral BRV administration from tablets

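### The SAP's two formulas for iv exposure always differ by 23 hours, and its iv PK Period has no exception for iv down-titration; both effects are descriptive and minor

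*SAP*

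**What the plan says.** **Duration formulas.** SAP 3.2.6 states: "The iv BRV exposure duration will be calculated separately in hours and days". The two formulas are introduced by "Duration of iv BRV exposure in days will be calculated using the following formula" and "Duration of iv BRV exposure in hours will be calculated using the following formula". Each subtracts the start date-time of the first iv dose from that of the last. The first then adds 1 day and the second adds 1 hour. The end point is "the start of last iv BRV infusion reported on the standard trial termination eCRF". Undosed days "which occur between the start and end date of the respective BRV formulation will be included in the exposure calculation", and the SAP's example applies this to both the days and the hours measure. The oral formulas, and the one for "The overall BRV duration (oral BRV and iv BRV exposure) in days", use calendar dates plus 1 day.

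**Reporting.** SAP 10.1 tabulates iv duration in hours and in days for the iv PK Period on the SS-iv, with a count of infusions running from 0 to 10. It adds: "Handling of missing study medication data is described in" 4.2.5. "For partial or missing date of last dose of study medication", 4.2.5 imputes a date but no clock time.

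**Period boundaries.** SAP 3.2.1 takes the last iv dose to be the last one in the study, except where the SAP notes otherwise. SAP 3.2.5 closes the iv PK Period, and opens Follow-up, 12 h after the start of the last iv treatment. For a child who down-titrates, Follow-up ends 12 h after the start of the last down-titration dose. SAP 2.3 gives the iv PK Period as 1 to 6 days, allows down-titration by iv with more than 10 consecutive iv doses, and counts down-titration as part of Follow-up.

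**The concern.** The two duration figures describe the same quantity for the same child from the same two inputs. A reader of the exposure table would expect one to convert into the other, and it does not. The relative discrepancy is largest for the 1 to 2 iv doses that SAP 2.3 makes the norm: a single infusion appears as both 1 day and 1 hour.

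The period rule matters only if a child is tapered by iv. The end of that child's iv PK Period moves to the end of the iv taper. SAP 10.2.1 assigns an AE to the period in which it began, so taper-phase TEAEs would appear under the iv PK Period in the by-period tables planned on the SS. The infusion count could run past its top row of 10. The Follow-up exposure summary in 10.1 covers oral BRV only, so it has no place for iv taper doses.

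**Working it through.** The documents state no exposure value to reproduce, so the check evaluates the rules as written.

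**1. The two iv formulas.** Let g be the hours from the first to the last iv start.

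- Hours formula: g + 1.
- Days formula, in hours: g + 24.
- Difference: (g + 24) − (g + 1) = 23 h, for any g.

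For k doses exactly 12 h apart, g = 12(k − 1). The last column shows the 12 h tail of 3.2.5: g + 12 = 12k.

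| Doses | g | Hours formula | Days formula | Gap | 12 h tail |
|---|---|---|---|---|---|
| 1 | 0 | 1 h | 24 h = 1.0 day | 23 h | 12 h = 0.5 day |
| 2 | 12 | 13 h | 36 h = 1.5 days | 23 h | 24 h = 1.0 day |
| 3 | 24 | 25 h | 48 h = 2.0 days | 23 h | 36 h = 1.5 days |
| 10 | 108 | 109 h | 132 h = 5.5 days | 23 h | 120 h = 5.0 days |

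The ratio of the two figures is 24 for one dose, 36/13 = 2.8 for two and 132/109 = 1.2 for ten. The ±2 h dosing window does not change the gap: two doses 10 to 14 h apart give 11 to 15 h against 34 to 38 h.

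**2. Against the calendar-day counts.** Take an IIB child without oral BRV and two doses 12 h apart. Overall BRV days are 1 for an 08:00 start and 2 for a 20:00 start, while iv days are 1.5 in both cases. Elapsed time and calendar days are different measures here and need different labels.

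**3. The period boundary.** For a taper given wholly by iv, the last down-titration dose is also the last iv dose in the study:

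Follow-up length = (last taper start + 12 h) − (last iv start + 12 h) = 0 h.

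SAP 5.1 would still count this child as starting down-titration in Follow-up. The phrase in 10.1 restricting the summary to the iv PK Period does not help, because 3.2.5 ends that period by the same last iv dose.

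**4. Illustration only**, assuming an all-iv taper that continues at 12 h intervals:

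- 4 doses, then 7 days: 4 + 14 = 18 infusions. The iv PK Period is 18 × 12 = 216 h (9 days) instead of 4 × 12 = 48 h.
- 10 doses, then 28 days: 10 + 56 = 66 infusions. The iv PK Period is 66 × 12 = 792 h (33 days) instead of 10 × 12 = 120 h.

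Both exceed the 6-day limit in 2.3 and the 0 to 10 infusion rows. If the taper is finished orally, only the part up to the last iv dose is misplaced.

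**The case against.** **On the formulas.** They are explicit and reproducible, and each adds one unit of its own scale, as inclusive counting often does. SAP 10.1 also gives the number of infusions and mean mg/kg dose, and lists the start and stop of each infusion, so actual dosing stays visible. All of this stands, and it limits the severity. It does not remove the defect: inclusive counting suits whole calendar days, whereas these formulas use clock times, and the SAP gives no reason for the different additions.

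**On the periods.** The intent can largely be recovered. Section 3.2.1 allows for exceptions, 3.2.5 refers to 2.3, and 2.3 puts down-titration in Follow-up. An iv taper is also an unlikely route: the child must stop BRV and be unable to take it orally, and down-titration is mandatory only after at least 4 doses. This too stands as a limit on importance. Followed literally, however, 3.2.5 contradicts 2.3.

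**Stronger readings that the documents do not support.**

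- *That iv days should be a calendar-date count.* The undosed-day rule does not favour this, because it covers both formulas. With a 12 h tail on the hours, a date count would replace the fixed gap by one that depends on the clock. Two doses would be 24 h against 1 day (gap 0) from a morning start, or against 2 days (gap 24 h) from an evening start.
- *That relative days and follow-up medications are misclassified during an iv taper.* SAP 3.2.3 reserves the plus sign for post-treatment days, and 3.2.6 defines study medication as iv BRV, which such a child is still receiving.
- *That the trial termination page is a faulty source.* Nothing in the documents shows this.
- *That the main safety results are affected.* Protocol 12.4.1.1 does name the iv PK Period for the primary safety variables on the SS-iv. The SAP's SS-iv AE incidence tables by age cohort and infusion duration, however, pool all periods.

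**Conclusion.** Both defects are in the text, and both are minor. The 23 h gap is exact for every child whose first and last iv start date-times are complete. It would differ only if days were programmed on calendar dates, which is not what the formula says. Neither addition agrees with the SAP's own 12 h tail.

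The period contradiction applies only to children down-titrated by iv. The documents do not give their number, which may be zero, and the 18- and 66-infusion cases are illustrations. The consequences are descriptive: SAP 3.1 plans no hypothesis tests, no rate uses these durations, and AE tables that pool all periods are unchanged.

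**What to change.** **Durations (3.2.6, 10.1).** Use one common tail in both formulas, for example the 12 h of 3.2.5, and derive days as hours divided by 24. Label the result elapsed time, distinct from the calendar-day counts for oral and overall BRV. Set it to missing when the time of the last dose is missing.

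**Periods (3.2.5, and the iv PK Period exposure summaries of 3.2.6 and 10.1).** Use the last iv dose before down-titration. Assign iv taper doses and events to Follow-up, limit the 0 to 10 row to iv PK Period infusions, and report iv taper exposure under Follow-up. Leave the plus-sign day rule in 3.2.3 and the follow-up medication rule in 6.3 as they are, or label those days explicitly.

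**Cost.** A short SAP edit and a re-derived exposure table. If any child was tapered by iv, also re-derived by-period tables and one added iv exposure summary for Follow-up. No new data are needed: Protocol 7.7 records the start and completion of every infusion, and SAP 5.1 already requires down-titration doses to be identified. The interim and final CSR outputs described in SAP 4.3.2 should use the same derivation. The drawback is that elapsed iv days will not match overall calendar days, which is why the labels matter.
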